### **5.2.2. Permitted drugs and treatments**

All unprohibited products and treatments are allowed.

## **5.3. Methods of control of compliance with procedures and subjects**

For the whole post-immunization follow-up period, the study subjects had to log in their volunteer's diaries information on the body temperature, any adverse events, and treatment with any medicinal drugs. At Visits 2–8, the investigator reviews the volunteer's diary and assesses the incidence and severity of adverse reactions, as well as the volunteer's compliance with the rules of concomitant therapy.

Additionally, the investigator assesses the regularity of the subject's visits to the trial site. The investigator can withdraw the subject from the study in case of subject's non-compliance with the requirements to concomitant therapy or if the study subject was not able to comply with the medical recommendations, in the investigator's opinion.

Strictly confidential. Proprietary Information.  
[name]

Study protocol does not provide for self-administration of the study products, the single dose immunization is performed at the trial site. The trial site personnel has to ensure that all the procedures related to the study product accountability are complied with (see Section 3.7).

As some of the study procedures (e.g., recording of AEs, blood sample collection, urine sample collection, vital signs measurement, physical examination, neurological examination, etc.) are performed by the investigator or another authorized personnel of the trial site at the study Visits, no methods of compliance control for such procedures are required.

## 6. EFFICACY EVALUATION

### 6.1. List of efficacy parameters

Parameters of immunogenic activity and efficacy are listed in Section 3.1.

### 6.2. Methods and terms of evaluation, recording and analysis of efficacy parameters

Evaluation of efficacy parameters includes the following procedures:

- serum antibody to antigens titer test: influenza virus type A — H1N1, influenza virus type A — H3N2, influenza virus type B — Yamagata and Victoria lineages prior to and at Day 21 after immunization;
- influenza and ARI incidence recording within 6 months after immunization;
- evaluation of severity and duration of reported cases of influenza and ARI, complications.

#### **Serologic testing (serum antibody titer test):**

Immunological efficacy (antigenic activity) of the vaccine is evaluated by its ability to induce the specific immune response, which can be identified under laboratory conditions by serum antibody titer to each antigen.

Antibody titer is determined using the hemagglutination inhibition reaction (HAIR), the method recommended by the WHO for influenza vaccine efficacy evaluation. The study is conducted at the central laboratory. As an additional method for 150 volunteers (50 volunteers in each group), a microneutralization assay is planned (the data will be used to evaluate seroprotection). The detailed description of the study methods is provided in the laboratory guide.

Blood samples for antibody titer test and calculation of mean geometric antibody titer will be collected for determination of background antibody titer after the immunization (Visit 0, Screening) and evaluation of functional immune reaction three weeks after immunization (Visit 7, Day 22±1).

Study parameters:

- The share of subjects achieving seroconversion (the number of volunteers with antibody titer [of at least 1:40] increased more than 4-fold versus baseline [assessed by HAIR]) for antigens: influenza virus type A — H1N1, influenza virus type A — H3N2, influenza virus type B — Yamagata and Victoria lineages.

Strictly confidential. Proprietary Information.  
[name]

- Coefficient of increase of mean geometric antibody titer (antigens H1N1, H3N2, Yamagata and Victoria lineages) (assessed by HAIR).
- Geometric mean of serum antibody to antigens titer (assessed by HAIR): influenza virus type A — H1N1, influenza virus type A — H3N2, influenza virus type B — Yamagata and Victoria lineages.
- Seroprotection: share of subjects achieving protective antibody titer (1:40 and more, assessed by HAIR and microneutralization test) to antigens H1N1, H3N2, Yamagata and Victoria lineages.

The detailed instruction on blood and serum sampling, labeling of tubes, storage and transportation of samples is presented in a separate laboratory guide provided by the central laboratory.

#### **Influenza and ARI incidence recording:**

Influenza and ARI incidence recording is performed during 6 months after immunization by means of follow-up and telephone calls to the study subjects.

A case of influenza and ARI is considered as a case of flu-like symptoms (according to: ECDC TECHNICAL DOCUMENT Protocol for case-control studies to measure pandemic and seasonal influenza vaccine effectiveness in the European Union and European Economic Area Member States / European center for Disease Prevention and Control, 2009):

*if a subject seeks physician's advice regarding unexpected occurrence of*

*- at least one of four systemic symptoms: 1) chills or fever, 2) distress, 3) headache, 4) myalgia and*

*- - of at least one of three respiratory symptoms: 1) cough, 2) sore throat, 3) respiratory distress.*

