**The expected benefits from the use of the study drug and the comparator drug:**

For a long time, trivalent influenza vaccines have been successfully used on the territory of the Russian Federation and around the world as an efficient and safe measure for prevention of influenza. The development of a quadrivalent vaccine containing strains of two lines of influenza B viruses will provide for a more reliable protection of the population, thus, increasing the immunization efficiency. Several trivalent vaccines (Fluarix Tetra, FluQuadri, Afluria, etc.) produced in Europe and the USA have already been successfully used in the world. In the Russian Federation, such drugs are currently not available.

---

Strictly confidential. Proprietary Information.  
[name]

Quadrivalent vaccine induces high-level specific anti-influenza immunity formation. Post-vaccination protective effect usually comes in 8–14 days, and the immunity retains up to 12 months, including elderly people. Protective anti-influenza antibody titers are detectable among 75–95 % of the vaccinated people of different age.

Development of the first Russian quadrivalent vaccine will help improve the effectiveness of vaccination and significantly improve the cost-effectiveness of preventive immunization.

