***Visit 7 (Day 22±1 after immunization):***

The following procedures are performed at Visit 7:

- Physical examination.
- Body temperature measurement ( $t^\circ$ ).

Strictly confidential. Proprietary Information.  
[name]

- Measurements of vital functions (pulse, SBP, DBP).
- Laboratory investigations:
  - Blood hematology (hemoglobin, RBCs, hematocrit, platelets, WBC and WBC differential [neutrophils, lymphocytes, monocytes, eosinophils, basophils], ESR).
  - Blood biochemistry (glucose, urea, creatinine, total bilirubin, total protein, ALT, AST, AP).
  - Urine test with sediment microscopy (specific density, protein, sugar, RBC, WBC).
  - Blood collection for IgE test.
  - Blood collection for serology (serum antibody titer).
  - Urine test for pregnancy (only for female subjects).
- Interviewing on ARI symptoms within the period.
- Review and return of the volunteer's diary.
- Assessment for exclusion criteria.
- Recording of concomitant therapy.
- Recording adverse events and intercurrent disorders.

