***Systemic reactions:***

1. Increase of body temperature over 37 °C
2. Malaise
3. Headache
4. Sleep disturbance
5. Appetite disturbance
6. Nausea
7. Vomiting
8. Abdominal pains
9. Stuffy nose

---

Strictly confidential. Proprietary Information.  
[name]

10. Cough
11. Pharynx hyperaemic
12. Increased sweating
13. Tremor
14. Myalgia, arthralgia.

The nature and duration of immunization reactions in vaccinated subjects is compared upon interpretation of all study materials. An analysis of this data will make it possible to formulate a conclusion and resolve the issue of tolerability of study vaccines.

The course of the post-immunization period is assessed as smooth or complicated. Complicated course of the post-immunization period is considered as integration of intercurrent diseases after immunization. The absence of intercurrent diseases is considered as smooth post-immunization period. Fever responses were classified by temperature increase as follows: mild (low-grade fever up to 37.5 °C), moderate (temperature rise from 37.6 °C to 38.5 °C), and severe (temperature rise above 38.6 °C).

Local immunization reactions are classified as mild, moderate, and severe. Erythema without infiltration up to 50.0 mm in diameter at the injection site or infiltration up to 25.0 mm in diameter is estimated as a mild local reaction; erythema with a diameter more than 50.0 mm or an infiltrate with a diameter 26.0 to 50.0 mm was estimated as a moderate local reaction; infiltration more than 50.0 mm in diameter was estimated as a severe local reaction (Methodological Guidelines MU 3.3.2.1758-03 "Methods for determination of quality indicators of immunobiological products for prevention and diagnostics of influenza"). When the reaction is free of redness and/or infiltration, the reaction severity is accepted as indeterminate.

Local reactions will be assessed in all subjects, since local reactions were directly related to the administration of the vaccine.

Occurrence of general symptoms on the first 3 days after (and even on the day of immunization) may be associated with immunization (systemic reactions). However, it does not rule out their causal relationship with diseases, accidentally occurring within the first days of post-immunization period.

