- Seroprotection: share of subjects achieving protective antibody titer (1:40 and more) to antigens H1N1, H3N2, Yamagata and Victoria lineage, based on assessment at Day 21 after immunization (Visit 7).

The shares of subjects achieving seroprotection will be presented with two-sided exact 95 % confidence intervals. Intergroup comparisons will be performed based on the exact Fisher test, as well as based on logistic regression with the vaccine as a fixed factor and the baseline antibody titer log as a covariate. The clinical center, sex, and age will also be considered as potential factors of the model.

- Incidence of influenza and ARI based on assessment 180±5 days after immunization (Visit 11).

Incidence of the disease will be presented with the respective two-sided 95 % confidence interval for therapeutic groups. The parameter will be analyzed using the Kaplan-Meier survival method (time to the first episode of the disease).

- Evaluation of severity and duration of reported cases of influenza and ARI, symptoms and complications will be presented descriptively for therapeutic groups.

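### The secondary influenza/ARI endpoint has no at-risk start day, so illness before the vaccines are expected to protect counts as an efficacy event and uses up the volunteer's only counted episode

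*Combined protocol and SAP*

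**What the plan says.** Section 6.2 (Influenza and ARI incidence recording) states: "Influenza and ARI incidence recording is performed during 6 months after immunization by means of follow-up and telephone calls to the study subjects". The list of procedures at the start of Section 6.2 gives the same window: "influenza and ARI incidence recording within 6 months after immunization". For the analysis, Section 8.1 (Secondary study endpoint) states: "The parameter will be analyzed using the Kaplan-Meier survival method (time to the first episode of the disease"). The assessment point is Day 180±5.

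On the onset of protection, Section 1.3 (expected benefits) states: "Post-vaccination protective effect usually comes in 8–14 days, and the immunity retains up to 12 months".

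The case definition in Section 6.2 has three parts. The volunteer must seek a physician's advice about an unexpected occurrence. There must be "at least one of four systemic symptoms: 1) chills or fever, 2) distress, 3) headache, 4) myalgia". There must also be at least one of cough, sore throat or respiratory distress.

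Section 7.2 lists systemic vaccine reactions, among them temperature above 37 °C, malaise, headache, myalgia and cough. Section 1.3 (potential risks) adds sore throat as an infrequent reaction. On timing, Section 7.2 says: "Occurrence of general symptoms on the first 3 days after (and even on the day of immunization) may be associated with immunization". It then rules that, when an infectious illness such as ARI arises in the first days, the general symptoms are taken out of the systemic reactions recorded over the first five days.

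**The concern.** By the protocol's own account, illness in roughly the first one to two weeks mostly arises before the vaccine can act. Such illness says little about differences in protection between the vaccines, yet it enters the efficacy count on equal terms with later illness. Two consequences follow.

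- **Dilution.** If the vaccines differ in protection, early cases that are equally frequent in all arms pull the comparison towards no difference.
- **Loss of the informative event.** The analysis uses time to first episode. A volunteer with a cold on Day 4 has had the counted event, and influenza in Month 3 is then ignored.

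A further question is attribution. Systemic reactions and the case definition share symptoms, and the one rule that separates them works in one direction only: it removes early ARI symptoms from the reaction count and does not remove reactions from the ARI count.

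Efficacy is in the study title and objective, and influenza/ARI incidence, with the severity and duration of those cases, is the only clinical-disease outcome in the plan. It is a secondary endpoint.

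**Working it through.** **1. Is a start day defined anywhere?** Sections 6.2 and 8.1 give no lag, time origin, exclusion of early cases or sensitivity window. The first ARI interview is at Visit 7 (Day 22±1; Section 3.2) and is described as "Interviewing on ARI symptoms within the period", so its recall period includes Days 0–14. Counting from Day 0 is therefore the natural reading, although no sentence states it.

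**2. The plan's own sizing figure.** Section 8.2 sizes only seroconversion. With reference 60 %, test 59 %, margin 15 %, one-sided 2.5 % and power 80 %:

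n = (1.960 + 0.842)² × [0.60 × 0.40 + 0.59 × 0.41] / (0.15 − 0.01)² = 7.849 × 0.4819 / 0.0196 ≈ 193

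193 / 0.95 = 203.2, which rounds up to 204 per group. The stated figures reproduce. None of these inputs involves influenza/ARI, so they do not change. No sample size is stated for influenza/ARI.

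**3. Share of follow-up before protection.** Inputs are the 8–14 days from Section 1.3 and the 180 days of follow-up. Constant risk is an assumption.

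- 8/180 = 4.4 %
- 14/180 = 7.8 %
- Across the ±5-day visit window: 8/185 = 4.3 % to 14/175 = 8.0 %

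**4. Expected number of early cases.** The documents give no attack rate, so 5 %, 10 % and 20 % over six months are assumptions. With n = 204 per group, early cases = 204 × [1 − (1 − p)^(L/180)], where L is 8 or 14 days.

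| Assumed attack rate p | All cases per group | Cases before protection |
|---|---|---|
| 5 % | 10.2 | 0.5–0.8 |
| 10 % | 20.4 | 1.0–1.7 |
| 20 % | 40.8 | 2.0–3.5 |

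**5. Dilution.** Let w be the share of risk before protection and assume no difference between arms in that period. Then observed RR = w × 1 + (1 − w) × true RR. For a true RR of 0.70:

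- w = 0.044: 0.044 + 0.956 × 0.70 = 0.713
- w = 0.078: 0.078 + 0.922 × 0.70 = 0.723

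If early risk were three times the later risk (an assumption with no source in the documents), w = 24/196 = 0.122 to 42/208 = 0.202, and the observed RR would be 0.74–0.76.

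**6. What the change would gain.** As an illustration, compare 204 (Group A) with 408 (Groups B and C) at two-sided 5 %, with a 10 % attack rate and a true RR of 0.70. Power is about 19.0 % counting from Day 0 (RR diluted to 0.723) and about 20.2 % counting after Day 14 (both rates multiplied by 166/180). The comparison is weak either way, and the gain in power is about one percentage point.

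**7. Symptom overlap.** Section 7.2 and Section 1.3 side by side with the case definition:

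- Systemic part: temperature rise, headache and myalgia appear in both; malaise corresponds closely to distress.
- Respiratory part: cough (Section 7.2) and sore throat (Section 1.3) appear in both.

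A set of listed reactions can therefore supply the symptoms in both parts. The third condition, seeking advice for something unexpected, still has to be met.

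**The case against.** **Counting from vaccination is a legitimate choice.** All three arms receive an active vaccine and are randomised, so illness before protection should be balanced between them. Section 1.3 says protection *usually* comes in 8–14 days, so some volunteers will be protected within that window. All of this stands. It makes the effect a small dilution rather than a bias in favour of one arm. It does not supply a time origin, and it does not restore the later episodes that the first-episode rule discards.

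**Little depends on the endpoint.** It is secondary, it has no stated hypothesis or margin, and no sample size was derived for it. This also stands and limits the weight of the point.

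**Onset dates are available, so early cases could be separated at analysis.** That is true, but a window chosen after unblinding would look data-driven.

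**A reader might infer a sizeable bias against the quadrivalent vaccine** from the Phase I systemic-reaction rates in Section 1.2 (20.7 % versus 3.6 %). The documents do not support that step:

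- The general reactions named there are temperature rise, malaise, headache, nausea and myalgia/arthralgia. None is respiratory, and Table 1 shows no respiratory term among related events.
- The rates correspond to 6/29 and 1/28, with a reported p of 0.102. Saline placebo showed 10.3 %.
- Volunteers with intercurrent illness in the first five days were excluded from that analysis.
- Section 1.3 expects the same safety profile as the trivalent vaccines and puts sore throat below 1/100, that is, at most about 2 of 204 volunteers per group (204 × 0.01 = 2.04). Fewer of them would seek advice.

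**A reader might also infer that case-finding is most intense on Days 1–5**, because visits are daily. Section 3.2 schedules the ARI interview only at Visit 7 and the telephone calls. Visits 2–6 record reactions, adverse events and intercurrent disorders. A symptom mentioned at a compulsory visit is not clearly care-seeking for an unexpected occurrence.

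**Conclusion.** The point holds as a modest, inexpensive improvement to a secondary endpoint. The plan counts influenza/ARI over six months after immunization as time to first episode and sets no at-risk start day, against its own statement on the onset of protection. At constant risk, 4–8 % of counted time and cases fall before protection, and a true risk ratio of 0.70 would appear as about 0.71–0.72. Both figures rest on constant risk and on no difference between arms before protection. If the vaccines do not differ in protection, there is nothing to dilute.

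The loss of a later episode after an early one does not depend on the constant-risk assumption. The overlap between reactions and case symptoms is real, and the separation rule in Section 7.2 does not protect the ARI count. The care-seeking and unexpected-occurrence conditions limit this, and no numerical bias can be derived from the documents. The seroconversion analysis and the 193/204 per group are untouched.

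**What to change.** In Sections 6.2 and 8.1, before unblinding:

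1. Make the main influenza/ARI efficacy analysis count first episodes with onset after Day 14 and up to Day 180±5.
2. Start the Kaplan-Meier clock at Day 14. Keep volunteers with an earlier episode at risk for their first episode after Day 14.
3. Report episodes on Days 0–14 separately, by arm, as intercurrent diseases or adverse events.
4. Give the count from Day 0 as a sensitivity analysis.

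**Cost.** Wording only. Section 7.3.1 already records the onset of adverse events, and the planned contacts continue after an early episode, so no new visits, samples or volunteers are needed. Counted follow-up falls by 14/180, about 8 %, with slightly fewer events. Volunteers lost before Day 14 contribute no time to the main analysis but remain in the sensitivity analysis.

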***Telephone calls (Visits 8–11):***

Telephone calls are made on Day 43±5 (Visit 8), Day 64±5 (Visit 9), Day 122±5 (Visit 10), Day 180±5 (Visit 11) and included the following procedures:

- Interviewing on ARI symptoms within the period.
- Assessment for exclusion criteria.
- Recording of concomitant therapy.
- Recording adverse events and intercurrent disorders.

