#### **Evaluation of severity and duration of reported cases of influenza and ARI, complications:**

When recording a case of influenza or ARI, a study doctor will perform an evaluation of its duration, making additional telephone calls, where necessary, and determine its severity. In this study, a case with at least one of the complications listed below will be considered severe:

- the necessity of hospitalization,
- influenza-associated pneumonia,
- influenza-associated cardiovascular disorder,
- death.

---

Strictly confidential. Proprietary Information.  
[name]

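### The influenza/ARI case definition requires a physician consultation that no listed contact records, the label claims influenza without a virological test, and onset dates after Visit 7 would rest largely on recall

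*Combined protocol and SAP*

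**What the plan says.** **Case definition.** Section 6.2 finds cases over six months through follow-up and telephone calls. A case requires at least one of four systemic symptoms and at least one of three respiratory symptoms, and it applies "if a subject seeks physician's advice regarding unexpected occurrence of" those symptoms. The source named there is, by its title, a protocol for case-control studies.

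**Contacts.** Visit 7 (Day 22±1) and the calls on Days 43, 64, 122 and 180 (each ±5) include "Interviewing on ARI symptoms within the period". The calls also include "Recording adverse events and intercurrent disorders". No listed step asks whether a physician was consulted or obtains a record of a consultation.

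**Diary.** Visit 7 in Section 3.2 lists "Review and return of the volunteer's diary". Section 5.3 says: "For the whole post-immunization follow-up period, the study subjects had to log in their volunteer's diaries information on the body temperature", together with adverse events and medication, and has the investigator review the diary at Visits 2–8, although Visit 8 is a call. Section 7.2 ends routine thermometry at Visit 7, with later measurements depending on the volunteer's condition.

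**Severity and analysis.** The severity list in Section 6.2 includes "influenza-associated pneumonia" and a cardiovascular item worded the same way. It also lets the study doctor make extra calls when a case is recorded. Section 8.1 presents incidence by group with a 95 % confidence interval and a Kaplan-Meier analysis of time to first episode. It does not define the onset date or its source.

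**The concern.** The trial questions every volunteer about symptoms, then defines the case by a behaviour that the questions do not capture. Someone who had fever, myalgia and cough and stayed at home meets both symptom criteria. On the literal wording that person is not a case, although the information is in hand. If sites instead treat a report to the study doctor as seeking advice, the same episode is a case. The plan leaves each site to choose.

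The undefined rule can also work differently over time. Volunteers are seen daily on Days 1–5 and reached only by telephone after Visit 7.

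Two further gaps affect the same endpoint. The label refers to influenza, but Table 2, Section 6.2 and Table 3 contain no virological test on illness; the serology measures vaccine response at screening and Visit 7. And the Kaplan-Meier analysis needs onset dates, yet one section takes the diary away at Visit 7, just before the long intervals between calls. This is the trial's only clinical efficacy endpoint, and efficacy is in the title.

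**Working it through.** **1. What the plan sizes.** The only sample size in the plan is for seroconversion (Section 8.2). With 60 % on reference, 59 % on test, a 15 % margin, one-sided 2.5 % and 80 % power:

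n = (1.96 + 0.84)² / (0.15 − 0.01)² × (0.60×0.40 + 0.59×0.41) = 193 per group.

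Then 193 / 0.95 = 203.2, rounded up to 204 per group and 612 in total. This reproduces the plan. No event count, power or success rule is given for influenza/ARI.

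**2. Where an episode goes.** Take a volunteer who reports qualifying symptoms at a call and did not consult.

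| Source | Result |
|---|---|
| Section 3.2, telephone calls | Symptoms elicited; event recorded as adverse event or intercurrent disorder |
| Section 7.3.1 | Onset and resolution times collected where possible |
| Section 6.2, literal reading | Not an endpoint case |
| Section 6.2, if the study doctor counts as the physician | Endpoint case |
| Section 8.1 | No rule to choose between the two readings |

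**3. Intervals between contacts.** Nominal gap = difference between scheduled days. Maximum gap = latest day of the later contact minus earliest day of the earlier one.

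| Interval | Nominal (days) | Range with windows (days) |
|---|---|---|
| Visit 7 to 8 | 43 − 22 = 21 | 15–27 |
| Visit 8 to 9 | 64 − 43 = 21 | 11–31 |
| Visit 9 to 10 | 122 − 64 = 58 | 48–68 |
| Visit 10 to 11 | 180 − 122 = 58 | 48–68 |

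The two long intervals cover 116 of the 158 days from Day 22 to Day 180: 116/158 = 73 %.

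**4. Illustration of counts (assumed inputs).** The documents give no attack rate or consulting rate. Assume 10 % of a group of 204 has a symptomatic episode, about 20 people, and that 20–50 % consult. Then 4–10 are counted. With relative standard error ≈ 1/√cases, 20 cases give 22 %, 10 give 32 % and 4 give 50 %.

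**5. Illustration of power (assumed inputs).** Section 8.1 plans no test here, so this only gives a scale. Compare 204 on test with 408 on pooled comparator, with a 30 % relative reduction, two-sided 5 %, and the consulting share s multiplying both rates. Power = Φ[(d − 1.96·SE₀)/SE₁], with SE₀ from the pooled proportion and SE₁ from the separate ones. For a 20 % attack rate and s = 1: d = 0.20 − 0.14 = 0.06, SE₀ = 0.0329, SE₁ = 0.0313, power 44 %.

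| Attack rate | s = 100 % | 70 % | 50 % | 30 % |
|---|---|---|---|---|
| 10 % | 22 % | 16 % | 12 % | 8 % |
| 20 % | 44 % | 30 % | 22 % | 14 % |
| 30 % | 66 % | 47 % | 33 % | 20 % |

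This holds the relative reduction equal for attended and unattended episodes, which is a further assumption.

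**The case against.** A reader might infer that episodes without a consultation are discarded. The documents do not say so. Every call records adverse events and intercurrent disorders, Section 7.3.1 collects their onset times, and no rule drops a reported episode. Exclusion from the endpoint is the literal consequence of one unclear sentence. This objection stands, and the point is therefore about an unreconciled definition.

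A reader might also infer that duration and severity depend on just two late calls. Section 6.2 allows additional calls for a recorded case, and Section 7.2 allows later temperature measurements. That stands too, but those calls start only once the case is known, so they do not help to fix an onset already weeks past. A consulted case could be dated from a medical record, which the plan neither requires nor excludes.

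On the diary, the synopsis and Table 2 use the word follow-up for Visits 2–7, so Section 5.3 could be read as ending there. Its reference to Visit 8 does not fit that reading. The text is at best ambiguous and needs aligning.

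Medically attended flu-like illness is a coherent endpoint, Section 6.2 openly describes flu-like symptoms, and the plan never claims laboratory confirmation. Widening the definition trades specificity for count and could dilute a vaccine contrast. Also, the relative standard errors above compare two different quantities. These points stand. They argue for reporting both versions, not for replacing one with the other.

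Finally, the schedule is the same in all groups of a randomised, double-blind trial. The documents do not support an inference of bias toward one arm.

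**Conclusion.** The concern holds as a mismatch between definition and data collection on a secondary endpoint with no power calculation. As written, the endpoint either leaves out symptomatic episodes that the trial has already elicited or depends on each site's reading of who the physician is. Its label goes beyond what is measured. Onset dates for episodes without a consultation would rest largely on recall across intervals of nominally 58 days, and at most 68, that make up 73 % of the time after Visit 7.

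The consequences are fewer counted events, imprecise times to first episode and an over-broad label. The size of the loss is not fixed by the documents: 4–10 counted out of about 20 per group, and power of 14 % against 44 % at the lowest consulting share considered, both rest on assumed rates. The interval lengths and the textual conflicts rest on the documents alone. Neither the comparison between arms nor the seroconversion endpoint is put at risk. The change is worth making because it is cheap, not because the trial fails without it.

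**What to change.** - **Sections 6.2 and 8.1:** record at each contact whether a physician was consulted, and state whether the study doctor counts. Report all episodes that meet the symptom criteria and, beside them, the medically attended subset.
- **Label:** use *influenza-like illness* for the endpoint in Sections 3.1, 6.2 and 8.1 and in the conclusions. In the severity list, replace *influenza-associated* with *associated with the episode*.
- **Diary:** reconcile Visit 7 in Section 3.2 with Sections 5.3 and 7.2, so that volunteers keep a simple diary of symptom onset and end dates to Visit 11 and read it out at the calls.
- **Onset:** state in Section 8.1 that the recorded symptom onset date is used in the Kaplan-Meier analysis.

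The cost is wording, one extra question per contact and a diary kept for longer. Symptoms are already elicited, so no added visits, scheduled calls or tests are needed. The downside is that self-reported episodes are less specific; the attended subset preserves the present definition for anyone who prefers it.
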